# Table 3. Operational definitions of study variables in the selected databases

#### Table 3. Operational definitions of study variables in the selected databases

Variable	Role	Operational definition				
		•				
Abbreviations: AIDS = acqu	ired immunodeficiency syndrome; AL	C = absolute lymphocyte count; ALT =				
alanine aminotransferase; Al	NC = absolute neutrophil count; aRMN	A = additional risk minimisation measures;				
AST = aspartate aminotransf	Ferase; ATC = Anatomical Therapeutic	c Chemical; CABG = coronary artery				
bypass graft; cs = convention	nal synthetic; CV = cardiovascular; D	MARD = disease-modifying antirheumatic				
drug; EBV = Epstein-Barr vi	rus; HDL = high-density lipoprotein;	HBV = hepatitis B virus; HCV = hepatitis				
C virus; HIV = human immu	nodeficiency virus; HPV = human pap	pillomavirus; HZ = herpes zoster;				
ICD-10 = International Class	ICD-10 = International Classification of Disease, 10 th Revision; KSHV = Kaposi sarcoma-associated					
herpesvirus; LDL = low-density lipoprotein; MBR = (Swedish) Medical Birth Register; MI = myocardial						
infarction; MTX = methotres	xate; NHIFA = National Health Insura	nce Fund Administration (of Hungary);				
NPR = (Swedish) National Patient Register; PCI = percutaneous coronary intervention; PsA = psoriatic						
arthritis; RA = rheumatoid at	rthritis; SAP = statistical analysis plan	; TB = tuberculosis; TG = triglycerides;				
UC = ulcerative colitis; VTE	=venous thromboembolism.					

#### 9.3.3. Duration of tofacitinib therapy

Duration of tofacitinib therapy will be defined as the time from the date of the index tofacitinib dispensing to the date of discontinuation of tofacitinib. The operational definitions for duration of tofacitinib therapy will be further elaborated in the SAP and made specific to each database. For example, for NHIFA, the Hungarian administrative claims database, the following proxy will be used to estimate duration: time between two prescription dispensings of tofacitinib, allowing for a grace period of a pre-determined length (e.g., 90 days) before being considered to have discontinued tofacitinib. The length of the grace period will be determined during development of the SAP.

#### 9.3.4. Average daily dose

Average daily dose (ADD) will be calculated in milligrams per day, starting from the index date and according to the variables available in the database, for the following pre-specified time intervalsij:

- Week 0 through Week 7 (from Day 1 to Day 56);
- Week 8 through Week 15 (from Day 57 to Day 112);
- Week 16 through Week 23 (from Day 113 to Day 168);
- Week 24 through Week 31 (from Day 169 to Day 224);
- Week 32 through Week 39 (from Day 225 to Day 280); and

<sup>jj The intervals will provide estimates for ADD over time. Some patients, for example those diagnosed with UC and prescribed an induction dose of 10 mg BID, may see a dose decrease over time showing the change from induction to maintenance therapy. However, given that patients may begin maintenance either at Week 8 or 16 and that patients may start and stop their medication anytime throughout follow-up, the periods are not labeled as induction or maintenance.

• Week 40 through Week 47 (from Day 281 to Day 336kk).

For each of these pre-specified time intervals, ADD will reported as a continuous and categorical variable:

- Up to 5 mg ADD;
- >5 mg to 11 mg ADD;
- >11 mg to 15 mg ADD;
- >15 to 20 mg ADD; and
- >20 mg ADD.

ADD will be further stratified by:

- Approved indication, or by the indication groups: "PsA or RA" and "UC";
- Presence of  $\geq 1$  VTE risk factor prior to tofacitinib initiation;
- Use of an alternative therapy (i.e., biologic) in the 12 months prior to tofacitinib initiation; and
- VTE Reporting Period (1, 2, and 3), depending on the objective.

The operational definitions for ADD will be further elaborated in the SAP and made specific to each database. For example, in Sweden, daily dose will be estimated by the defined daily doses (DDDs) or the strength of a single unit. Days' supply will be estimated by the number of DDDs in the respective dispensation.

**Note:** The objectives and sub-objectives that contain an ADD component will *not* be assessed in Hungary or the Netherlands. The Hungarian administrative claims database is unable to estimate ADD, either directly or by proxy, due to how tofacitinib is captured in the database. In the high-budget impact medication dataset of the PHARMO Database Network (Netherlands), neither ADD nor the number of pills per prescription is captured.

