# 7. RATIONALE AND BACKGROUND

Tofacitinib citrate (Xeljanz®) is an oral Janus kinase inhibitor approved by the European Commission (EC) in March 2017 as an immediate-release film-coated tablet (5 mg), taken twice daily (BID), for the treatment of adults with moderate-to-severe active rheumatoid arthritis (RA) who have had inadequate response or intolerance to one or more disease-modifying antirheumatic drugs (DMARDs). The EC subsequently approved a prolonged-release film-coated tablet (11 mg), taken once daily (QD), in December 2019. RA is a chronic systemic autoimmune disease characterized by inflammation and progressive destruction of joints. Despite a number of treatment options available, many patients do not sustain remission. In clinical trials, patients treated with 5 mg of tofacitinib BID, in combination with methotrexate (MTX), showed significantly reduced disease activity scores and improved physical functioning and general health status as compared to patients on placebo. The approved dose of tofacitinib for the treatment of moderate-to-severe active RA is 5 mg BID or prolonged-release 11 mg QD, which should not be exceeded, in combination with MTX; it may also be given as monotherapy in the case of intolerance to MTX or when treatment with MTX is inappropriate.

In June 2018, tofacitinib 5-mg tablet (immediate-release) was approved by the EC, in combination with MTX, for the treatment of active psoriatic arthritis (PsA) in adults with inadequate response or intolerance to a prior DMARD therapy. PsA is an inflammatory arthritis occurring in between 6%-42% of patients with psoriasis. In clinical trials, patients treated with 5 mg of tofacitinib BID, in combination with a non-biologic DMARD, achieved significantly improved clinical response and physical functioning over the 6- and 12-month study periods. The approved dose of tofacitinib for the treatment of active PsA is 5 mg BID, which should not be exceeded.

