Finally, in July 2018, tofacitinib 5-mg tablet and 10-mg tablet (immediate release) were approved by the EC for the treatment of moderately-to-severely active ulcerative colitis (UC) in patients with an inadequate response, a loss of response, or an intolerance to conventional therapy or a biologic agent. UC is a bowel disease characterized by inflammation and ulcers in the colon and rectum. In clinical trials, patients treated with 5 mg or 10 mg of tofacitinib BID were more likely to achieve and/or maintain a clinical response and remission of their condition as compared to patients in the placebo group. At the time of initial approval, the doses of tofacitinib for the treatment of moderately-to-severely active UC were 10 mg BID for induction (up to a 16-week period) and 5 mg BID for maintenance, which should not be exceeded.

The following table summarizes the date tofacitinib was approved by the EC and the approved dose for each of the 3 approved indications as of June 2021.

Indication	Date approved by the EC	Approved dose
RA	March 2017	5 mg immediate-release tablets BID
	December 2019	11 mg prolonged release tablets QD
PsA	June 2018	5 mg immediate-release tablets BID
UC	July 2018	5 mg or 10 mg immediate-release tablets BID

Table 1.	Summary of appro	oved indications and	dosages for tofacitinib
----------	------------------	----------------------	-------------------------

Abbreviations: EC = European Commission; PsA = psoriatic arthritis; RA = rheumatoid arthritis; UC = ulcerative colitis.

**Note:** BID is an abbreviation for "bis in die," which in Latin means twice a day; QD is an abbreviation for "quaque die," which in Latin means once a day.

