## 9.3. Variables

### 9.3.1. Outcomes

The primary outcomes of interest will be (see Table 3 for operational definitions):

- The demographics, comorbidities, and prior and current medications (including prior use of biologics) of tofacitinib patients;d,e
- Prescribers' adherence to the tofacitinib aRMMs, specifically:
  - Compliance to the recommended posology per indication and duration of use, as measured by:f
    - ADD of tofacitinib therapy, calculated in 8-week intervals from Week 0 through Week 47, and reported in the following categories:
      - Up to 5 mg ADD;
      - >5 to 11 mg ADD;

<sup>c This exclusion criterion will primarily apply to those patients who received their index tofacitinib prescription for an indication within the first 3 months after approval of that indication.

<sup>d The data sources are unable to reliably ascertain severity of hepatic impairment and renal impairment.

<sup>e In GKV claims, outpatient diagnoses are reported quarterly.

<sup>f The study outcomes that contain an ADD component will *not* be assessed in Hungary or the Netherlands. The Hungarian administrative claims database is unable to estimate ADD, either directly or by proxy, due to how tofacitinib is captured in the database. In the high-budget impact medication dataset of the PHARMO Database Network (Netherlands), neither ADD nor the number of pills per prescription is captured.

- >11 to 15 mg ADD;
- >15 to 20 mg ADD; and
- >20 mg ADD;

Note that within these reporting intervals and categories, ADD will also be reported by approved indication or by the indication groups: "PsA or RA" and "UC", presence of  $\geq$ 1 VTE risk factor prior to tofacitinib initiation, and prior use of an alternative therapy (i.e., biologic) in the 12 months prior to tofacitinib initiation; depending on the objective, outcomes will be stratified by reporting period;e,g

- The proportion of patients with an ADD of >11 mg during any of the 8-week follow-up intervals and no evidence of a diagnosis for UC; and
- The proportion of patients with an ADD of ≥15 mg in Weeks 16-23, Weeks 24-31, Weeks 32-39, and/or Weeks 40-47 of follow-up with evidence of a diagnosis for UC but no use of an alternative therapy (i.e., biologic) *prior to* tofacitinib initiation;

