The PDR, maintained by the National Board of Health and Welfare, contains all prescribed and dispensed medication for patients in Sweden. Coverage of prescriptions is close to 100%, however, inpatient administrations are not captured and there is only partial capture of drugs administered in hospital outpatient visits. Information included in the PDR include basic demographic characteristics such as age, sex, and residency, as well as medication-specific information such as the prescribed / dispensed drug (e.g., ATC code, International Non-proprietary Names [INN]), prescription dispensing date, pack size, dispensed amount, formulation, dosage, prescribing healthcare practitioner, and costs. The PDR is updated monthly. The Swedish MBR was established in 1973 and is managed by the National Board of Health and Welfare (NBHW). The register covers 100% of births and stillbirths of at least 22 gestational weeks since July 2008 (and of at least 28 gestational weeks before July 2008) in Sweden thereby facilitating the identification of tofacitinib exposure during pregnancy. There are no data on elective terminations or spontaneous abortions in the register. The register covers information such as gestational duration, self-reported smoking status during pregnancy, diagnoses during pregnancy, date of birth, delivery complications, diagnoses of the mother and the child, Apgar score, low birthweight, head circumference and survival. The data for the previous calendar year are usually available in December of the following year. Access to the register data for scientific research is decided by the NBHW through a standard application procedure and is assessed on a case-by-case basis.

The NCR was started in 1958 and is managed by the NBHW. The registry records all newly diagnosed tumours and blood cancers diagnosed by clinical, morphological, or other laboratory examinations, as well as cases diagnosed at autopsy. Since the mid-1980s, there are six regional registries associated with the oncological centres in each medical region of Sweden where the registration, coding, and major check-up and correction work is performed. The register includes information on patient characteristics, tumour characteristics, diagnosis, and date and cause of death. Data are updated on an annual basis with a lag time of approximately 13 months. Applications for data access are sent to the National Board of Health and Welfare and processed by a pre-defined data permit process.

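### The Swedish dose example in Section 9.3.4 returns the DDD or the tablet strength instead of the prescribed daily dose, so it cannot carry the over-dose outcomes

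*Protocol*

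**What the plan says.** Protocol Section 9.3.4 defines average daily dose (ADD) in six 8-week intervals and gives one worked illustration, for Sweden: "in Sweden, daily dose will be estimated by the defined daily doses (DDDs) or the strength of a single unit". It continues: "Days' supply will be estimated by the number of DDDs in the respective dispensation". The sentence before the illustration says that "The operational definitions for ADD will be further elaborated in the SAP and made specific to each database". No milligram value for the DDD is given, and no rule for supplies that overlap.

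Three outcomes in Section 9.3.1 depend on the result:
- "The proportion of patients with an ADD of >11 mg during any of the 8-week follow-up intervals", without a UC diagnosis.
- ADD of at least 15 mg from Week 16 in UC patients with no prior biologic.
- ADD above 10 mg from Week 16 in UC patients with a VTE risk factor and no prior biologic.

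Section 9.9 says what ADD should read: 10 mg for 5 mg BID and 20 mg for 10 mg BID. It treats more than 20 mg in the first eight weeks as inappropriate use. A footnote to Section 9.3.4 expects the fall from UC induction to maintenance to be visible.

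Section 9.4.1 lists the content of the Prescribed Drug Register (PDR), including "prescription dispensing date, pack size, dispensed amount, formulation, dosage".

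**The concern.** The number of DDDs is itself milligrams divided by the DDD. Using it as days' supply makes the dose calculation circular: every dispensation returns the same constant. The other option, one tablet's strength, is blind to how many tablets are taken per day. A measure of prescribers' adherence to posology must at least respond to the prescribed posology, and per dispensation this one does not.

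Hungary and the Netherlands are excluded from all ADD outcomes, so only Sweden and Germany contribute. Table 4 expects about 3400 Swedish patients against 1111 German ones, so Sweden is the larger source. If over-dosing is under-counted there, the report could present a measurement artefact as compliance. If supply is carried over between dispensations, it could instead report non-compliance that did not occur.

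**Working it through.** **Inputs from the protocol.** The two Swedish proxies (Section 9.3.4). Tablet strengths in Section 7: "tofacitinib 5-mg tablet and 10-mg tablet (immediate release) were approved by the EC", and a "prolonged-release film-coated tablet (11 mg), taken once daily (QD), in December 2019". The thresholds >11, ≥15 and >10 mg (Section 9.3.1). The expected ADD values (Section 9.9).

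**Assumptions, not in the protocol.** The DDD, written D, is taken from 5 to 20 mg, with 10 mg as the central case. Refills are regular: 56 tablets every 28 days, two a day.

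**Step 1. The plan's own figures.** Tablet strength × tablets per day: 2 × 5 = 10 mg and 2 × 10 = 20 mg. Both match Section 9.9.

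**Step 2. DDD route, one dispensation of M mg.** Days' supply = M / D. Dose = M / (M / D) = D, for any M. With D = 10:
- 56 × 5 mg = 280 mg, 28 days, 10 mg/day.
- 56 × 10 mg = 560 mg, 56 days, 10 mg/day. The truth is 28 days at 20 mg/day.

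**Step 3. Unit-strength route.** The result is 5, 10 or 11 mg. So 5 mg BID reads 5 mg (true 10) and 10 mg BID reads 10 mg (true 20).

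**Step 4. 8-week intervals with refills, D = 10, DDD route.**
- *Overlap not added.* 5 mg BID and 10 mg BID both read 10 mg in every interval.
- *Overlap added.* For 10 mg BID, one supply is active on Days 1-28 and two on Days 29-56: (28 × 10 + 28 × 20) / 56 = 15 mg in Weeks 0-7, then 20 mg in each later interval.
- *Overlap added, 10 mg BID for 16 weeks, then 5 mg BID.* The Day 85 dispensing is credited with 56 days, to Day 140. Days 113-140 read 10 + 10 = 20 mg and Days 141-168 read 10 mg. Weeks 16-23 average (28 × 20 + 28 × 10) / 56 = 15 mg; the truth is 10 mg. With no prior biologic, this patient falsely meets ≥15 mg.

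With unit strength as the daily dose, overlap added and D = 10, 5 mg BID still reads 5 mg.

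**Step 5. Range of D, DDD route.**

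| D (mg) | Any regimen, overlap not added, per day covered | 10 mg BID, overlap added |
|---|---|---|
| 5 | 5 | 7.5, then 17.5, then 20 |
| 10 | 10 | 15, then 20 |
| 11 | 11 | 15.52, then 20.04 |
| 20 | 20 | 20 throughout |

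At D = 5, each 10 mg pack is credited with 560 / 5 = 112 days, so supplies accumulate: (28 × 5 + 28 × 10) / 56 = 7.5, then (28 × 15 + 28 × 20) / 56 = 17.5, then 4 × 5 = 20. At D = 11, supply is rounded to 51 days: (51 + 28) × 11 / 56 = 15.52, then 102 × 11 / 56 = 20.04.

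Without overlap, the >11 mg threshold is met by nobody when D ≤ 11 and, per day covered, by everybody when D > 11.

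**Step 6. Milligrams dispensed over elapsed days.** 10 mg BID: 2 × 560 / 56 = 20 mg in every interval. The step-down patient in Weeks 16-23: 2 × 280 / 56 = 10 mg. Both are correct.

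**The case against.** The text is introduced as an example and the definitions are deferred to the SAP. Section 9.3.4 names two proxies but does not say how dispensations combine into an interval value. Section 9.9 already warns that a days' supply proxy may misclassify exposure and that Swedish ADD will be imprecise, and it shows that the intended measure separates 10 mg from 20 mg.

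A reader might go further and infer that Swedish ADD can never exceed 11 mg, so that the over-dose outcomes are zero by construction. The protocol does not support that. It needs a DDD of at most 11 mg and overlaps not added, and neither is stated. With overlaps added, 10 mg BID does reach 20 mg from Week 8. With D = 20, no overlap and averaging over all 56 days rather than covered days, regular 5 mg BID reads 10 mg and 10 mg BID reads 20 mg, as they should. The >10 mg UC outcome is not strictly emptied even by an 11 mg ceiling, since an 11 mg unit exceeds 10. Nor can distorted duration or discontinuation be inferred: Section 9.3.3 leaves the Swedish duration rule to the SAP.

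These limits stand. What does not stand is the defence that this is only detail for the SAP. The protocol states what daily dose and days' supply will be, this is its only dose algorithm for any country, and a general caveat about imprecision does not cover a proxy that is constant across regimens. Section 9.7 also says that major changes to primary endpoint definitions go through a protocol amendment.

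**Conclusion.** The point holds in conditional form. Per dispensation, the Swedish example returns the DDD or a tablet strength and contradicts the 10 mg and 20 mg readings in Section 9.9. That part rests on algebra and needs no outside figure.

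The effect on the outcomes depends on D and on overlap handling:
- D ≤ 11 mg, overlaps not added: the >11 mg and ≥15 mg outcomes are empty in Sweden.
- D = 10 mg, overlaps added: first-interval ADD for 10 mg BID is 5 mg too low, and Weeks 16-23 can be 5 mg too high after a step-down at Week 16.
- D = 20 mg, overlaps not added, DDD route per day covered: everyone reads 20 mg, including patients on 5 mg BID.

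The interval figures assume regular 28-day refills of 56 tablets. Germany's ADD is outside this example. No judgement on any dose is made.

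**What to change.** Replace the Swedish example in Section 9.3.4, and carry the change into the SAP:
- Define interval ADD as milligrams dispensed divided by days covered, allocated to the 8-week intervals.
- Take days covered from the interval between dispensings, capped, with a stated rule for the last dispensing. Use the PDR dosage field instead only if it is confirmed to record the daily regimen; the list in Section 9.4.1 does not settle whether it means regimen or strength.
- State how overlapping supply is treated.
- Do not use the number of DDDs as days' supply for the Swedish outcomes that Table 3 defines by overlapping supply (biologics and potent immunosuppressants taken with tofacitinib). At D = 10, it credits a 28-day supply of 10 mg BID with 56 days.

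The cost is one paragraph in the protocol and its counterpart in the SAP. Dispensing date, pack size and dispensed amount are already listed as available. The downside is that the last dispensing needs an imputed length.

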#### 9.4. Data sources

This study will use the following European databases, which were selected based on anticipated sample size, data availability and completeness, and/or geographic location to increase the generalisability of the study results to the EU:

<sup>kk The last 29 days of a 365-day year will not be captured in an 8-week interval.

- Sweden: National health registers: The National Patient Register (NPR); the Prescribed Drug Register (PDR); the Swedish Medical Birth Register (MBR); the National Cancer Registry (NCR); and the Swedish Cause of Death Register (CDR);
- Hungary: National Health Insurance Fund Administration (NHIFA), an administrative claims database;
- The Netherlands: PHARMO Database Network; and
- Germany: GKV claims, an administrative claims database.

# 9.4.1. Sweden: The National Patient Register, the Prescribed Drug Register, the Swedish Medical Birth Register, the National Cancer Registry, the Cause of Death Register

Health care in Sweden is primarily government-funded and managed at the national, regional, and local level. Only a small proportion of the population (6%) also have some type of supplementary private health insurance. In most regions, there is no formal gatekeeping and patients may contact specialists directly. In Sweden, patients with inflammatory rheumatic diseases like RA and UC are typically treated by hospital-based specialists as opposed to general practitioners (GPs). The current study will utilize four large Swedish registers linked via patients' personal identifications numbers: the NPR, the PDR, the Swedish Pregnancy Register, and the NCR.

The NPR includes information regarding inpatient and outpatient non-primary (i.e., specialist) encounters across Sweden; outpatient GP encounters are not captured in the NPR. Beginning in 1987, coverage for inpatient admissions became nationwide and is near 100%. Coverage for outpatient non-primary care began nationwide in 2001 and is around 87% (although it may be higher for somatic care such as rheumatology). Key variables include diagnosis, surgery, external causes of injury (E-codes), age, sex, hometown, hospital, specialty, and information related to hospital admissions and discharges (e.g., dates, main and contributory diagnoses, mode of discharge). Information on patient anthropometric data (e.g., height, weight, body mass index) is not available nor are laboratory test results (e.g., ALC, blood lipid levels) or clinical measurements (e.g., blood pressure). A number of diagnoses, including RA, have been reported to have high positive predictive values in the inpatient register; in recent studies, the reported positive predictive value in the NPR was 91% for RA and 79% for UC. The NPR is updated annually.

The PDR, maintained by the National Board of Health and Welfare, contains all prescribed and dispensed medication for patients in Sweden. Coverage of prescriptions is close to 100%, however, inpatient administrations are not captured and there is only partial capture of drugs administered in hospital outpatient visits. Information included in the PDR include basic demographic characteristics such as age, sex, and residency, as well as medication-specific information such as the prescribed / dispensed drug (e.g., ATC code, International Non-proprietary Names [INN]), prescription dispensing date, pack size, dispensed amount, formulation, dosage, prescribing healthcare practitioner, and costs. The PDR is updated monthly. The Swedish MBR was established in 1973 and is managed by the National Board of Health and Welfare (NBHW). The register covers 100% of births and stillbirths of at least 22 gestational weeks since July 2008 (and of at least 28 gestational weeks before July 2008) in Sweden thereby facilitating the identification of tofacitinib exposure during pregnancy. There are no data on elective terminations or spontaneous abortions in the register. The register covers information such as gestational duration, self-reported smoking status during pregnancy, diagnoses during pregnancy, date of birth, delivery complications, diagnoses of the mother and the child, Apgar score, low birthweight, head circumference and survival. The data for the previous calendar year are usually available in December of the following year. Access to the register data for scientific research is decided by the NBHW through a standard application procedure and is assessed on a case-by-case basis.

The NCR was started in 1958 and is managed by the NBHW. The registry records all newly diagnosed tumours and blood cancers diagnosed by clinical, morphological, or other laboratory examinations, as well as cases diagnosed at autopsy. Since the mid-1980s, there are six regional registries associated with the oncological centres in each medical region of Sweden where the registration, coding, and major check-up and correction work is performed. The register includes information on patient characteristics, tumour characteristics, diagnosis, and date and cause of death. Data are updated on an annual basis with a lag time of approximately 13 months. Applications for data access are sent to the National Board of Health and Welfare and processed by a pre-defined data permit process.

The Cause of Death Register (CDR) is managed by the NBHW. It contains data from 1961 and is updated annually. There is also a historical register of causes of death for the years 1952–1960. The register includes all deaths that have occurred in Sweden, including deaths of non-Swedish citizens. Key variables include age, sex, country of birth and residency, date of death, cause of death (ICD-9/10 codes have been used since 1988), and intent (in cases of injury or poisoning), medical procedures (if death occurred within 4 months after surgery), and autopsy. Stillbirths are not included in the register. The register is updated annually for the cause of death are available in the register earlier. Access to the register data for scientific research is decided by the NBHW through a standard application procedure and is assessed on a case-by-case basis.

Most of the Swedish registries are updated yearly, and it can take 6-9 months to receive a data extraction. As a result, there is a lag in data availability of approximately 14-21 months.

